4.5.5 Analysis of covariance (ANCOVA) for change from baseline

Analysis of covariance (ANCOVA) is used for endpoints examining the change from baseline to week t (See Section 4.8.2 and Table 11 for details of endpoints). In this model, the change from baseline (at time point t) is a function of the treatment group (fixed effect) and the baseline measure (covariate). The following model will be used:

$$D_{t,ij} = intercept + \beta Y_{0,ij} + \tau_i + error_{ij}$$

where, $D_{t,ij} = Y_{t,ij} - Y_{0,ij}$, the week t change from the baseline of subject j in treatment group i; $Y_{0,ij}$ is the baseline measure of subject j in treatment group i; $Y_{t,ij}$ is the week t measure of subject j in treatment group i; τ_i is the mean effect of treatment group i; intercept, β and τ_i are unknown parameters to be estimated from the data.

Ordinary least squares (OLS) will be used to estimate the model's parameters along with two-sided 95% Confidence Intervals (CIs).

4.5.6 Kaplan-Meier curve and estimates for time-to-event analysis

Kaplan-Meier plots of time to rescue will be displayed by treatment group. Unless otherwise specified, the plot will be presented only when there are at least 5 events in one treatment group. Additionally, a table will accompany the plot and will display the Kaplan-Meier estimates of the cumulative proportion (with 95% confidence interval based on Greenwood's method when applicable) of patients with event at specific time points by treatment group. If the estimated lower bound of 95% confidence interval is below 0 or the estimated upper bound of 95% confidence interval is over 1, then it will be restricted to 0 or 1 respectively.

Time to rescue is defined as the time (in days) from the first dose date after randomisation to the date at which the patient first meets the following rescue criterion: (which is confirmed),

- i. FPG > 240 mg/dL (13.3 mmol/L) for the period after Visit 2 to and including Visit 8 (Week 0 to 12) OR
- ii. FPG > 200 mg/dL (11.1 mmol/L) for the period after Visit 8 to and including day of Visit 9 (Week 12 to 24) OR
- iii. HbA1c > 8% for the period after Visit 9 to and including Visit 12 (Week 24 to 52)

Time to rescue will be censored at the earliest of discontinuation of study medication/study, or study completion, or time of insulin start (for those subjects who received rescue treatment without confirmed rescue criteria).

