1.3 Number of patients

To demonstrate non-inferiority of dapagliflozin plus metformin or dapagliflozin plus saxagliptin plus metformin to glimepiride plus metformin for changes from baseline to week 52 in HbA1c within a non-inferiority margin of 0.30% - assuming a standard deviation 1.0%, and at a 1-sided significance level of 0.025 - 290 evaluable patients will be needed in each treatment group to provide approximately 95% power (given a true difference of zero between dapagliflozin or dapagliflozin plus saxagliptin and glimepiride). The non-inferiority margin of 0.3% as well as a common standard deviation of 1.0% were selected based on information from earlier, similarly designed studies. Assuming that 5% of patients do not have a post-baseline assessment, a total of approximately 930 patients (310 patients per treatment arm) need to be randomised. Moreover, if 30% of screened patients fail to meet screening criteria, a total of 1329 patients need to be screened.

A hierarchical testing procedure will be followed to control type 1 error rate of 0.05. Dapagliflozin plus saxagliptin plus metformin will be tested for non-inferiority first. If dapagliflozin plus saxagliptin plus metformin is non-inferior to glimepiride plus metformin then dapagliflozin plus metformin will be tested for non-inferiority.

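### SAP 4.5.6: untransformed Greenwood intervals for the Kaplan-Meier rescue proportions sit too low if an arm has few events; complementary log-log limits would largely cure this in a descriptive table

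*SAP*

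**What the plan says.** Section 4.5.6 of the SAP plans a Kaplan-Meier plot of time to rescue by treatment group. An accompanying table gives the cumulative proportion with an event at time points that the section does not list, each "with 95% confidence interval based on Greenwood's method when applicable". A boundary rule follows. It starts "If the estimated lower bound of 95% confidence interval is below 0", adds the matching case for an upper limit that "is over 1, then it will be restricted to 0 or 1 respectively". On display, "the plot will be presented only when there are at least 5 events in one treatment group".

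The formal comparison is elsewhere. Section 4.8.2 and Table 11 assign time to rescue to a Cox model, with a Wilcoxon test if proportional hazards fails. Section 4.3.1 places that comparison sixth in the testing order. For the endpoints that are proportions, section 4.5.7 switches to an exact 95% interval when any group has fewer than 5 responders.

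**The concern.** Greenwood's formula gives a variance; the interval also needs a scale. Limits on the log-log or logit scale stay within 0 to 1, and limits on the log scale can overshoot only one end. A rule for overshoot at both ends therefore describes the untransformed interval, estimate ± 1.96 standard errors.

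That interval is symmetric, whereas the sampling distribution of a small proportion is skewed. When few events are observed by chance, both the estimate and its standard error are too small, so the upper limit falls short. The table would then understate how high the rescue risk in an arm could be. Section 4.5.7 guards against small counts and section 4.5.6 does not: its plot needs 5 events in only one group, so other groups and earlier time points can have fewer.

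**Working it through.** **Inputs.** From section 1.3: "290 evaluable patients will be needed in each treatment group to provide approximately 95% power" and "approximately 930 patients (310 patients per treatment arm) need to be randomised". The patient numbers come from the HbA1c calculation, "within a non-inferiority margin of 0.30" and "assuming a standard deviation 1.0" (both in HbA1c percentage points).

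**The plan's own figure first.** n = 2 × (1.960 + 1.645)² × 1.0² / 0.30² = 288.8, so 289. At 290 per group, 0.30 / √(2/290) − 1.960 = 1.65, which is 95.1% power. The stated size reproduces. 290 / 0.95 = 305.3, so 306, against 310 planned; 310 × 0.95 = 294.5, so 295 is also used in the examples.

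**Interval formulas.** Without censoring before the time point, with x events and p = x/n:

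- Untransformed Greenwood: p ± 1.96 √(p(1 − p)/n), reset to 0 or 1 if outside.
- Complementary log-log: 1 − (1 − p)^exp(±1.96 s), where s = √(p / ((1 − p) n)) / |ln(1 − p)|.
- Exact: Clopper-Pearson.

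**Examples at n = 295.**

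| Events | Untransformed | Log-log | Exact |
|---|---|---|---|
| 0 | 0 to 0 | none | upper limit 1.24% |
| 1 | 0 to 1.00% | 0.05 to 2.38% | 0.01 to 1.87% |
| 5 | 0.22 to 3.17% | 0.71 to 4.02% | 0.55 to 3.91% |

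For 5 events: p = 1.695%, standard error 0.7515%, so 1.695 ± 1.473. For 0 events the exact upper limit is 1 − 0.025^(1/295) = 1.24%. The untransformed lower limit is negative at 1 to 3 events and is already 0.04% at 4.

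**How a miss arises.** Take n = 290 and a true risk of 5/290 = 1.72%. Two events give an upper limit of 0.69 + 1.96 × 0.486 = 1.64%, below the truth; three give 1.03 + 1.96 × 0.594 = 2.20%, above it. The interval therefore misses on the high side whenever x ≤ 2, and P(x ≤ 2) = 12.2%.

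**Average over risks.** Exact binomial sums at n = 290, averaged over each range (nominal 2.5%):

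| True risk | High-side miss, untransformed |
|---|---|
| 1.5 to 3% | 7.9% |
| 3 to 5% | 5.9% |
| 5 to 7% | 5.1% |
| 10 to 20% | 3.8% |

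Log-log limits give 0.5 to 1.6% over the first three ranges. Single risks swing widely because counts are whole numbers: on a 0.05-point grid from 1.5 to 3%, the untransformed high-side miss runs from 4.5% to 14.2%. Its low-side miss is 0.3 to 1.3% up to 20 expected events, so the intervals are shifted downwards. With 310 per arm the results at given event counts agree to within about 0.1 point.

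**Censoring.** Simulated Kaplan-Meier estimates with 15% censoring (10,000 runs each) give high-side misses of 8.3%, 5.9%, 6.0%, 4.8% and 4.6% at 5, 10, 15, 20 and 30 expected events. The excess persists.

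**The alternative's own error.** Log-log limits miss on the low side in about 3.0 to 3.5% of cases on average at up to 30 expected events, and in up to 4.6% at single risks between 1.5 and 3%. With one event their upper limit exceeds the exact one by 2.38 − 1.87 = 0.51 point.

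**The case against.** The strongest reply is that nothing inferential depends on these intervals. They are per-arm limits in a table beside a plot, and time to rescue is compared by the Cox model. This stands. A reader might infer from the endpoint's place in the testing order that its test is affected; sections 4.8.2 and 4.3.1 do not support that.

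Sparse events are also assumed. The SAP gives no rescue rate and does not list the tabulated time points. The 5-event condition is a guard against sparse displays, not a forecast of them. From week 24 the criterion is HbA1c above 8%, in patients who enter at 7.5 to 10.5%, so counts at week 52 may be large. This stands too, although the guard needs only one group to reach 5 events.

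A reader might blame the reset to 0 or 1. It does not change coverage, since the true risk lies between 0 and 1, and in the 5-event example no limit is reset. It only shows which scale is meant.

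Finally, the qualifier on Greenwood's method may already exclude an arm without events. That is possible, but the section does not say what would be shown instead.

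**Conclusion.** The point holds as an optional refinement. Section 4.5.6 specifies an untransformed interval that sits too low at small cumulative proportions. At n = 290 without censoring the average high-side miss is about three times nominal at risks of 1.5 to 3% (7.9 / 2.5 = 3.2), twice at 5 to 7% (5.1 / 2.5 = 2.0) and 1.5 times at 10 to 20% (3.8 / 2.5). The size is conditional on few events in an arm at a tabulated time point, which is most plausible early, while the FPG criteria apply. It fades as events accumulate but has not vanished at 5 to 7%. An arm with no event gets a zero-width interval unless the qualifier covers that case.

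The plan is otherwise clear and reproducible here, and does not contradict itself. The Cox comparison, the testing order and the primary result are unaffected.

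**What to change.** In section 4.5.6, state that the pointwise 95% limits use Greenwood's variance on the complementary log-log scale. Delete the boundary sentence, which is then unnecessary. For an arm with no event by a time point, report an exact upper limit and say which number of patients it uses if some have been censored.

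The cost is one sentence and one program option. There is a small statistical price: a slightly raised low-side miss, and a somewhat high upper limit when an arm has a single event. At larger proportions the choice matters little.

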4.5.7 Analysis of proportions

Proportions endpoints will be analysed using logistic regression with the baseline measure as a covariate. The adjusted percentage with 95% CI, Odds Ratio with 95% CI and nominal p-values for the comparison of dapagliflozin or dapagliflozin plus saxagliptin vs glimepiride will be presented. The confidence intervals will be based on the profile likelihood method. When there are less than 5 responders in any treatment group, the unadjusted proportions (and difference), exact 95% confidence interval, and p-values from the Fisher's exact test (when applicable) will be provided.

4.5.8 Time spent below target HbA1c (<7% and <7.5%)

In order to calculate the time spent below HbA1c target (<7% and <7.5%), linear interpolation will be used to create a profile for the HbA1c values over time for each patient. The amount of time spent <7% (or <7.5%) will then be calculated (in days) from this profile. If there is more

than 1 segment where the patient is below target and then rebounds, the individual segment times will be added together.

Missing intermediate HbA1c values will not be imputed, the interpolation will proceed from the last available value to the next available value. If the week 52 value is missing, there will be no extrapolation of data to this timepoint.

Actual visit dates will be used to determine times between all visits. No time below target will be counted beyond 365 days (52 weeks).

Values recorded after rescue (for those who used rescue medication) or values collected more than 8 days after the last dose date (for patients who stayed more than 8 consecutive days off treatment) will be excluded from these calculations.

4.6 Missing data

4.6.1 Handling missing demographic and baseline characteristics data

For demographic and baseline characteristics, each variable will be analysed and/or summarized using the available data i.e. patients with missing data will be excluded from the summaries.

4.6.2 Handling missing efficacy data

Missing data can result from patients discontinuing the study prematurely or by missing intermediate visits or selected assessments while remaining in the study. To eliminate missing data, every effort will be made to obtain the protocol-required data for all scheduled study assessments for all enrolled patients. For efficacy analyses, the MMRM model assumes missing observations are missing at random (MAR). MAR means that the tendency of a data value to be missing depends only on the observed data, and not on the missing data. For example, if an HbA1c value is missing, it assumes this is not related to the missing data but to some of the observed data (response and covariates) (Ref (1)).

For the change in HbA1c and weight analyses using MMRM, values recorded after rescue treatment for those patients who used rescue medication or values collected more than 8 days after the last dose date for patients who stayed more than 8 consecutive days off treatment are excluded from the analysis. For the change in FPG analysis using MMRM, values recorded after rescue treatment for those patients who used rescue medication or values collected more than 1 day after the last dose date for patients who stayed more than 1 consecutive days off treatment are excluded from the analysis. For the change in SBP analysis using MMRM, values recorded after rescue treatment for those patients who used rescue medication or values collected more than 4 days after the last dose date for patients who stayed more than 4 consecutive days off treatment are excluded from the analysis.

The MMRM model assumes the time course of the endpoint values for patients who discontinue double-blind treatment or are rescued at a specific time point is consistent with the time course for patients ongoing at that time point.

Summaries of missing data by visit for HbA1c will be provided in order to explore this assumption (see Table 16 provided in Appendix IV).

When performing ANCOVA, the Last Observation Carried Forward (LOCF) method will be used for dealing with missing values i.e. if no Week 52 measurement is available, the last available earlier post-baseline measurement will be used except for the efficacy variable time spent below HbA1c target. For patients who started rescue medication prior to Week 52, their last post-baseline measurement taken prior to the date of the first dose of rescue medication will be used.

For the proportions endpoints regarding glycaemic control at week 52, all available data will be used but patients rescued prior to week 52 will be treated as treatment failures (non-responders). Subjects with missing information at week 52 (e.g. HbA1c, weight) will be counted as treatment failures. For the endpoints 'the proportion of patients with at least one episode of confirmed hypoglycaemia' and 'the proportion of patients with at least one episode of hypoglycaemia (symptomatic with blood glucose ≤70mg/dL [3.9mmol/L]), if the blood glucose value is missing for a patient with hypoglycaemia, they will not be counted as having a confirmed hypoglycaemic event.

Section 4.11 provides additional information regarding handling of missing or partial dates, inclusion of values, visit windowing, and values obtained post treatment.

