3.3 Other secondary efficacy variables

Other secondary efficacy variables are:

- Proportion of patients achieving HbA1c of <7% (and <7.5%) without confirmed hypoglycaemia at week 52
- Proportion of patients achieving HbA1c of <7% (and <7.5%) at Week 52
- Proportion of patients achieving individually agreed HbA1c targets at Week 52
- Proportion of patients achieving an HbA1c decrease of ≥1% with no weight gain at week 52
- Time spent below HbA1C target (<7%) (and <7.5%) during the 52-week double-blind treatment period
- Change in body mass index (BMI) from baseline to week 52
- Proportion of patients achieving weight reduction of $\geq 5\%$ from baseline to week 52
- Proportion of patients with weight gain $\geq 5\%$ from baseline to week 52
- Proportion of patients reporting at least 1 episode of any hypoglycaemia (confirmed = symptomatic + blood glucose ≤50 mg/dL, major, other hypoglycaemia) during the 52-week double-blind treatment period
- Change in waist circumference from baseline to week 52
- Change in systolic BP from baseline to week 52
- Proportion of patients reporting at least one episode of hypoglycaemia (symptomatic + blood glucose ≤70 mg/dL [3.9 mmol/L]), see section 4.9.6) during the double-blind treatment period

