4.3.1 Control of Type I error

The experiment-wise type I error will be controlled to a maximum of 5%. A hierarchical closed testing procedure will be employed such that key secondary endpoints will be considered for statistical significance (in terms of superiority) only if non-inferiority of the primary endpoint is concluded and that a key secondary endpoint will be considered for statistical significance only if the test ordered before it is found to be statistically significant. At each step, dapagliflozin plus saxagliptin added to metformin versus glimepiride added to metformin will be tested first followed by the test for dapagliflozin added to metformin versus glimepiride added to metformin except for the superiority tests of the primary endpoint and the endpoint of total body weight. The test of superiority for HbA1c will include only the comparison of dapagliflozin plus saxagliptin added to metformin versus glimepiride added to metformin. For total body weight, dapagliflozin added to metformin versus glimepiride will

be tested first followed by dapagliflozin plus saxagliptin added to metformin versus glimepiride added to metformin.

The following testing order will be followed for the overall type I error control:

- 1. Change from baseline in HbA1c at Week 52 (test for non-inferiority)
- 2. Proportion of patients reporting at least 1 episode of confirmed hypoglycaemia at Week 52 (test for superiority)
- 3. Change in total body weight from baseline to Week 52 (test for superiority)
- 4. Change from baseline in HbA1c at Week 52 (test for superiority of dapagliflozin plus saxagliptin added to metformin vs glimepiride added to metformin only)
- 5. Change in FPG from baseline to Week 52 (test for superiority)
- 6. Time to rescue at Week 52 (test for superiority)

The statistical comparisons will be done using a comparison-wise type I error of 5% (2-sided). For all other secondary variables and exploratory variables, nominal p-values will be reported without multiplicity controlled significance testing.

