4.8.2 Analysis of secondary and exploratory variables

All secondary endpoints will be analysed using the Full Analysis set including values prior to rescue treatment or discontinuation. For HbA1c, weight, BMI and waist circumference, values recorded after rescue treatment for those patients who used rescue medication or values collected more than 8 days after the last dose date for patients who stayed more than 8 consecutive days off treatment are excluded from the analysis. For FPG, values recorded after rescue treatment for those patients who used rescue medication or values collected more than 1 day after the last dose date for patients who stayed more than 1 consecutive day off treatment are excluded from the analysis. For SBP, values recorded after rescue treatment for those patients who used rescue medication or values collected more than 4 days after the last dose date for patients who stayed more than 4 consecutive days off treatment are excluded from the analysis.

The statistical testing of the primary and key secondary efficacy variables will proceed in a sequential manner. If for the primary comparison between dapagliflozin or dapagliflozin plus saxagliptin (added to metformin) treatment group and the glimepiride (added to metformin) treatment group, the upper limit from a 2-sided 95% CI for the difference in adjusted means is less than 0.30%, then the dapagliflozin or dapagliflozin plus saxagliptin will be non-inferior to glimepiride and all four key secondary efficacy variables will be tested for superiority at a 0.05 level (two-sided) as well as the superiority test of the primary efficacy variable. To protect the type I error rate of the hierarchical testing procedure, the interpretation of the statistical significance of treatment comparisons for each key secondary efficacy variable and the superiority test of the primary efficacy variable will be done using a step-wise procedure (described in Section 4.3.1).

A summary of each efficacy variable and associated analysis is provided in Table 11.

The analysis of the changes from baseline to week 52 for a) total body weight, b) FPG and c) SBP will be performed using the MMRM model (as described for the primary efficacy endpoint). Point estimates and 2-sided 95% CI will be calculated for the adjusted mean changes from baseline within each treatment group and between treatment groups together with the p-values corresponding to testing the hypotheses of no difference between

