The proportion of patients with at least one episode of confirmed hypoglycaemia, the proportion achieving HbA1c <7% (and <7.5%) without confirmed hypoglycaemia at week 52, the proportion achieving HbA1c <7% (and <7.5%) at week 52, the proportion achieving their individually agreed HbA1c targets at week 52, the proportion with at least one episode of any hypoglycaemia and the proportion with at least one episode of hypoglycaemia (symptomatic with blood glucose ≤70mg/dL [3.9mmol/L]) will be summarised by treatment group and compared between treatment groups using logistic regression with baseline HbA1c as a covariate (see section 4.5.7). The adjusted percentage with 95% CI, Odds Ratio with 95% CI and nominal p-values for the comparison of dapagliflozin or dapagliflozin plus saxagliptin vs glimepiride will be presented. The confidence intervals will be based on the profile likelihood method.

The proportion of patients achieving a \geq 5% weight reduction or \geq 5% weight gain will be summarised by treatment group and compared between treatment groups using logistic regression with baseline weight as a covariate.

The proportion of patients with an HbA1c decrease ≥1% with no weight gain at week 52 will be summarised by treatment group and comparisons between treatment groups (contrasts of each test combination vs the control) will be performed using a Pearson's Chi-Square test. Nominal p-values and asymptotic 95% CIs will be presented.

Descriptive summaries of change from baseline in HbA1c, FPG, weight, BMI, waist circumference and systolic BP over time (observed values), will be presented in addition to the analyses described above.

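### The rule in SAP 4.6.2 that missing Week 52 information counts as treatment failure has no stated endpoint scope and does not suit the ≥5% weight-gain proportion

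*SAP*

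**What the plan says.** Section 4.6.2 deals with missing data in the proportion endpoints in consecutive sentences. The first is limited in scope: "For the proportions endpoints regarding glycaemic control at week 52, all available data will be used but patients rescued prior to week 52" are scored as failures, which the SAP glosses as non-responders. The second has no such limit: "Subjects with missing information at week 52 (e.g. HbA1c, weight) will be counted as treatment failures". The third concerns two hypoglycaemia proportions and states how a missing glucose value is coded, namely as no confirmed event.

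Section 3.3 lists "Proportion of patients with weight gain" of at least 5% among the other secondary variables. Section 4.8.2 handles it in one sentence with weight reduction of at least 5%: both are "compared between treatment groups using logistic regression with baseline weight as a covariate". Table 11 also puts them in one row. A separate composite, an HbA1c decrease of at least 1% "with no weight gain at week 52 will be summarised by treatment group", also needs a Week 52 weight.

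Two further provisions matter. Section 4.8.2 states: "All secondary endpoints will be analysed using the Full Analysis set including values prior to rescue treatment or discontinuation". For weight, it drops values recorded after rescue or more than 8 days after the last dose. Section 4.3.1 places this endpoint outside the testing hierarchy: "nominal p-values will be reported without multiplicity controlled significance testing".

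**The concern.** A failure rule is coherent when the event is a success, because a patient without data is not credited with it. Weight gain is an unfavourable event, so the two words that 4.6.2 treats as equivalent pull apart. Non-responder turns a missing patient into one who did not gain weight, which favours the arm with more missing data. Failure turns the same patient into one who did gain, which mixes dropout and rescue with weight gain. If some patients gain and some Week 52 weights are missing at random, neither coding recovers the proportion that full data would show.

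Missingness need not be balanced. Rescued patients stay in the study on their visit schedule (1.2.4.2), but their later weights are set aside under 4.8.2 and so become missing by rule. Section 4.3 hypothesises a longer time to rescue on both test regimens. If that holds and other missingness is similar, more Week 52 weights would be missing on glimepiride. At stake is the estimate and nominal p-value for one secondary weight comparison, and possibly its direction.

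**Working it through.** **Plan's own figure.** No figure in the SAP bears directly on this point. The only one borrowed is the 290 evaluable patients per arm in 1.3, based on non-inferiority "within a non-inferiority margin of 0.30"% HbA1c, SD 1.0%, a true difference of zero and one-sided 0.025. It reproduces: n = 2 × (1.960 + 1.645)² × 1.0² / 0.30² = 288.8, so 289 per arm, and power at 290 is 95.1%.

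**Inputs that the SAP does not give.** It states no weight-gain rate and no Week 52 missing rate. The 5% in 1.3 refers to patients with no post-baseline assessment at all. The true gain rate p and missing fraction d below are therefore assumptions. Missingness is taken as independent of outcome.

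**Formulas.** The observed rate in an arm is:
- missing = no gain: p(1 − d)
- missing = gain: p(1 − d) + d

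With the same p in both arms, the spurious difference (test minus control) is p(d_control − d_test) under no-gain coding and −(1 − p)(d_control − d_test) under gain coding.

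**No true effect: p = 8% in both arms, d = 10% test and 20% control.**
- No gain: 0.08 × 0.90 = 7.2% versus 0.08 × 0.80 = 6.4%. Difference 0.8 points, odds ratio (0.072/0.928)/(0.064/0.936) = 1.13.
- Gain: 7.2% + 10% = 17.2% versus 6.4% + 20% = 26.4%. Difference −9.2 points, odds ratio (0.172/0.828)/(0.264/0.736) = 0.58.
- Chance of nominal significance at two-sided 0.05 with 290 per arm, counted in the direction of the shift only (2.5% with no distortion): about 6% for no-gain coding and about 77% for gain coding.
- With 15% missing in both arms, the rates are 6.8% versus 6.8% or 21.8% versus 21.8%. The odds ratio is 1.00 under either coding.

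**True effect: p = 2% test and 10% control (odds ratio 0.18).**

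| Missing, test / control | Missing = no gain | Missing = gain |
|---|---|---|
| 15% / 15% | 1.7% vs 8.5%, OR 0.19 | 16.7% vs 23.5%, OR 0.65 |
| 10% / 20% | 1.8% vs 8.0%, OR 0.21 | 11.8% vs 28.0%, OR 0.34 |
| 20% / 10% | 1.6% vs 9.0%, OR 0.16 | 21.6% vs 19.0%, OR 1.17 |

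Other assumed true rates (3% vs 12%, 5% vs 15%) show the same pattern. With equal missingness of 10% or 15%, no-gain coding leaves the odds ratio within about 0.01 of the truth, while gain coding moves it to between 0.55 and 0.63. With 20% versus 10% missing, gain coding gives 1.10 and 1.03 against true values of 0.23 and 0.30.

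**Effect on the test used.** Section 4.5.7 switches to unadjusted proportions and Fisher's exact test when any arm has fewer than 5 responders. In the last row of the table the expected test-arm count is 0.016 × 290 = 4.6 under no-gain coding and 0.216 × 290 = 62.6 under gain coding. The coding can therefore decide which analysis is reported.

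**The case against.** The best defence concerns scope. The sentence follows one confined to glycaemic-control proportions, and the word weight has a natural home in the HbA1c/no-weight-gain composite, where scoring a missing patient as a failure is coherent. A reader might infer that the SAP expressly applies the rule to weight gain of at least 5%. It does not; that application is only implied. This part of the defence stands. It does not remove the problem, because on the narrow reading the endpoint has no missing-data rule at all: 4.6.2 ties LOCF to ANCOVA and the missing-at-random assumption to MMRM.

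The second defence concerns direction. Section 4.6.2 glosses failures as non-responders, and 4.5.7 appears to use responders for patients with the event, so the text leans towards no-gain coding, where the distortion is small. That also stands as a matter of likelihood. It is still not stated for weight gain, whereas 4.6.2 does state the coding for the hypoglycaemia endpoints.

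The third defence concerns size and consequence. The large figures need gain coding and, when there is no true effect, unequal missingness. The endpoint carries only a nominal p-value, and the confirmatory weight conclusion rests on the MMRM of weight change. All of this is correct and limits the weight of the point.

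**Conclusion.** The point holds as a defect of scope and fit. The rule has no stated endpoint list, and its two descriptions of a missing patient give opposite codings for an unfavourable outcome.

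A reader might go further and conclude that the weight-gain comparison is biased, or that it would mainly reflect dropout and rescue. The SAP does not support that, since it gives neither a weight-gain rate nor a Week 52 missing rate by arm. The size depends on the coding and the missingness. Under the assumed rates with no true effect and 10% versus 20% missing, the spurious difference is 0.8 points with no-gain coding and 9.2 points with gain coding. With equal missingness and no true effect, neither coding shifts the odds ratio. A reversal of direction appears only with gain coding and more missing data in the test arm. All these results assume 290 per arm and missingness unrelated to outcome.

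The primary and key secondary tests are unaffected. This is a worthwhile improvement of low priority.

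**What to change.** In 4.6.2, limit the failure rule to favourable responder endpoints and name them: the HbA1c targets, the HbA1c/no-weight-gain composite and weight reduction of at least 5%. Exempt weight gain of at least 5%.

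For that endpoint, derive Week 52 status by multiple imputation from the repeated on-treatment weights, under the same missing-at-random assumption as the weight MMRM. Then apply the planned logistic regression with baseline weight. Table 1 schedules a weight at every visit, so no new data are needed. Add missing = gain and missing = no gain as sensitivity analyses, so that readers can see how far the result depends on the patients without a usable Week 52 weight. State also how the fewer-than-5 fallback in 4.5.7 is triggered for this endpoint, since imputed counts vary between data sets.

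The change should be made before unblinding. It costs a few sentences of SAP text and a small extra program, on an endpoint with a nominal p-value only.
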